5 ADVERSE EVENTS

Definitions

Adverse events (AEs)

Adverse events (AEs) will be recorded at each regular scheduled study visit or study phone contact in the patient record (source document) as well as on a specific AE form on the electronic CRF.

An AE is any untoward medical occurrence in a patient or clinical investigation patient administered a pharmaceutical product and which does not necessarily have a causal relationship with this treatment. An AE can therefore be any unfavorable and unintended sign (including an abnormal laboratory finding), symptom, or disease temporally associated with the use of a medicinal product, whether or not related to the medicinal product, e.g.:

Timing of Ileostomy Closure after Ileal Pouch Surgery

- any new diagnosis
- any symptom that requires medical clarification or leads to in-patient admission (surgery or accident)
- any suspected adverse drug reaction (ADR)
- any symptom that appears on the patient's medical records
- any event related in time with the application of the study medication and affecting the health of the patient (including laboratory value changes)

Serious Adverse Events (SAE)

A serious adverse event (experience) is any untoward medical occurrence that at any dose:

- results in death
- is life-threatening
- requires inpatient hospitalization or prolongation of existing hospitalization
- results in persistent or significant disability/incapacity

Non-serious adverse events are all AEs that do not fall into any of the above categories.

Expected Adverse Events (i.e. complications of procedures; definitions included):

- Wound infection: redness or purulence at the IPAA incision that required opening of the wound and or treatment with antibiotics
- Abdominal or pelvic abscess: abnormal abdominal or pelvic fluid collection detected by CT or other imaging in a patient with clinical evidence of infection
- IPAA radiologic leak: free or contained extravasation of luminal contrast from the IPAA in a patient without clinical signs of IPAA leak
- IPAA clinical leak: free or contained extravasation of luminal contrast from the IPAA in a patient with clinical signs of IPAA leak
- IPAA stenosis: more than a simple web that can be treated by digitation
- Small bowel obstruction (SBO): radiologic confirmed in a patient with clinical signs of SBO
- Ileus: inability to tolerate normal oral intake by 72 hours after IPAA or ostomy reversal and/or radiologically confirmed in a patient with clinical signs of ileus
- Venous Thromboembolism: new diagnosis of upper or lower extremity of mesenteric vein VTE or pulmonary embolism after IPAA or ostomy reversal

Timing of Ileostomy Closure after Ileal Pouch Surgery

- Lung or heart-related complications: include new diagnosis of cardiac arrhythmia, coronary artery disease, congestive heart failure, pneumonia, pneumonitis after IPAA or ostomy reversal
- Hemorrhage requiring transfusion: pRBC administered after IPAA or ostomy reversal
- High output ileostomy: Regular use of antiperistaltic drugs required to control ileostomy output volume
- Peristomal skin irritation: irritation of the peristomal skin that resulted in pain, interference with activities of daily living (ADL), or unplanned treatments
- Peristomal infection: peristomal cellulitis or abscess requiring incision and drainage or unplanned ostomy surgery or antibiotic therapy
- Ileostomy prolapse: ileostomy prolapse that interferes with ileostomy pouching and/or ADL or requires surgical treatment
- Ileostomy stenosis: ileostomy stenosis that causes ileostomy dysfunction and/or interferes with ADL or requires surgical treatment
- Ileostomy revision necessary: unplanned ileostomy surgical treatment required
- Ileostomy leakage: persistent or recurrent ileostomy appliance leakage that interferes with ADL and requires more than ordinary measure to control
- Ileostomy dysfunction: dysfunction of the ileostomy that causes extraordinary problems with output, pouching, intestinal blockages, or otherwise interferes with ADL more than is usual and expected.
- Reoperation: any unplanned reoperation within 6 months of IPAA surgery
- Readmission: Any unplanned hospital readmission within 6 months of IPAA surgery
- Postoperative complication occurrence will be assessed via medical record review, discussion with study surgeon, other care givers, and study patient and recorded (CRF-6) at an interval of every 1 month until 6 months after randomization. Postoperative complication severity will be scored according to the Clavien-Dindo (CD) classification of surgical complications (Dindo, 2004, **Table**) The Comprehensive Complication Index will be calculated for each patient at 6 months after randomization.

6 DOCUMENTATION AND REPORTING OF ADVERSE EVENTS

All adverse events will be treated at the discretion of each individual center. All adverse events will be followed to resolution or until determined to be permanent. Adverse events will be graded using the definitions below:

Timing of Ileostomy Closure after Ileal Pouch Surgery

Grade 1: Mild asymptomatic or mild symptoms; clinical or diagnostic observations only; intervention not indicated.

Grade 2: Moderate, minimal, local or noninvasive symptoms with intervention indicated; limiting age-appropriate instrumental ADLs (Activities of Daily Living).

Grade 3: Severe or medically significant symptoms but not immediately life-threatening; Hospitalization or prolongation of hospitalization indicated; disabling; limiting self-care ADL.

Grade 4: Life-threatening consequences; urgent intervention indicated.

Grade 5: Death related to AE.

Serious Adverse Events: All information regarding SAEs will be collected and recorded on a specific SAE form. To ensure patient safety, each SAE must also be reported to the University of Colorado, within 24 hours of learning of its occurrence.

An SAE is defined by an undesirable sign, symptom or medical condition defined as an event which is:

1. Fatal or life-threatening
2. Results in persistent or significant disability/incapacity
3. Requires inpatient hospitalization
4. Constitutes a congenital anomaly/birth defect,
5. Is medically significant, i.e., defined as an event that jeopardizes the patient or may require medical or surgical intervention to prevent one of the outcomes listed above.

The following has to be documented for each AE:

- Nature of the event
- Time of onset: date, time
- Concomitant treatment: product (generic name), indication, dosage, dosage interval, presentation, mode of administration, administration regimen
- Duration of the AE

Timing of Ileostomy Closure after Ileal Pouch Surgery

- Severity
- Seriousness
- Causality
- Outcome

Severity

The severity is evaluated as follows:

1. Mild: - event/symptom does not interfere with normal daily activities
2. Moderate: - event/symptom interferes with normal daily activities
3. Severe: - event/symptom prevents normal daily activities

Causality

The relationship between an AE and the research is classified by the following:

Certain

A clinical event, including laboratory test abnormality, is occurring in a plausible time relationship to the research, and which concurrent disease or other drugs or chemicals cannot explain.

Probable/Likely

A clinical event, including laboratory test abnormality, with a reasonable time sequence to the research, unlikely to be attributed to concurrent disease or other drugs or chemicals, and which follows a clinically reasonable response. **Possible**

A clinical event, including laboratory test abnormality, with a reasonable time sequence to the research, but which could also be explained by concurrent disease or other drugs or chemicals. **Unlikely**

A clinical event, including laboratory test abnormality, with a temporal relationship to the research which makes a causal relationship improbable, and in which other drugs, chemicals or underlying disease provide plausible explanations.

Conditional/Unclassified

A clinical event, including laboratory test abnormality, reported as an adverse reaction, about which more data are essential for a proper assessment or the additional data are under examination.

Not assessable / Unclassifiable

A report suggesting an adverse reaction, which cannot be judged because information is insufficient or contradictory, and which cannot be supplemented or verified.

Not related

There is sufficient information available to show that the event is unrelated to the research.

The **course and outcome** of the adverse event will be commented on as follows:

- 1) Recovered without sequelae
- 2) Not yet recovered
- 3) Recovered with sequelae
- 4) Fatal

Documentation and Reporting of Serious Adverse Events

On enrolment in the study, the patients will be instructed to contact the investigator if a serious or unexpected AE occurs, so that appropriate measures can be taken.

Any SAE (including death, irrespective of the cause) occurring during or for up to 14 days after the end of the study must be reported without delay, i.e. within five days, by telephone and by fax to the principal investigator of the study organization or his designee, irrespective of its relationship with the research(minimum information required: investigator's name/study center, patient number, patient initials, date of first dose, date of last dose, date of event, description of event, causality assessment, and countermeasures).

Address:	Principal investigator	[contact]
Dept. of Surgery [name]	[name]	[contact]

A specific AE documentation form will be provided to the investigators (see appendix). In case of an SAE, this should be completed by the physician as an initial report, and sent (via fax) to the principal investigator. The report must contain a detailed description of the symptoms observed and the concomitant treatment administered. Furthermore, the investigator must comment on a possible causative relationship between the AE and the trial medication. Each SAE must be followed until it is resolved or can be explained satisfactorily.

In accordance with drug safety and national requirements, the study PI will inform the Data and Safety Monitoring Board (DSMB) of the study and will make sure that the involved persons will obtain adequate information. Also the local principal investigator will inform the local Ethics Committee.

Timing of Ileostomy Closure after Ileal Pouch Surgery

The following instructions must be heeded:

In the case of an intolerable SAE, the patient must, at the decision of the investigator, be withdrawn from the clinical trial, and symptomatic treatment must be administered. The measures taken must be recorded on the electronic CRF.

In accordance with local legislation, the investigators will submit copies of the final SAE-report to the Regulatory Authorities concerned, if necessary.

7 WITHDRAWAL OR STOP OF STUDY CRITERIA

Criteria in individual cases

Any patient can withdraw from the study at any time without personal disadvantages and without having to give a reason. The time of withdrawal, the results available up to that time, and, if known, the reason for withdrawal must be documented on the electronic CRF.

The investigator can also discontinue the study after considering the risk-to-benefit ratio, if he/she no longer considers the further participation of the patient justifiable. The date of and the primary reason for the withdrawal as well as the observations available at the time of withdrawal are to be documented on the electronic CRF.

Reasons leading to the **withdrawal** of a patient can include the following (primary reason must be determined):

- inclusion criterion not fulfilled or exclusion criterion fulfilled; coming to knowledge after recruitment
- patient's request
- technical or logistical reasons (e.g. a change in place of residence, not referred by family physician, etc.)
- other reasons (noting reason)

Criteria for the termination of the whole study

If serious safety concerns arise, the coordinating investigator can terminate or interrupt the study by agreement with the sponsor. If new information on the risk-to-benefit ratio of the treatment methods used in the study is obtained in the meantime, the coordinating investigator reserves the right to interrupt or terminate the project by agreement with the sponsor. Premature termination is also possible if the coordinating investigator, or the investigators and the sponsor if patient recruitment is insufficient and cannot be expedited by appropriate measures.

8 DATA SAFETY MONITORING

Data Safety Management Board: An independent Data and Safety Monitoring Board (DSMB), comprised of 2 independent surgeons and 1 biostatistician, has been established and will meet at the start of the study and at months 6 and 12 after enrollment begins. The chairman and site investigators will be masked to study outcomes during the course of the trial. Only the study biostatistician and DSMB members will have access to the study outcomes for monitoring purposes during the course of the study.

Stopping Endpoints: At their first meeting, the DSMB will decide how they wish to monitor the study. Typically, a DSMB will monitor all aspects of a study to ensure its scientific integrity, including patient screening and accrual, follow up, performance of individual centers, data acquisition and quality issues, adverse events, and outcomes. At the first meeting, we will also determine their desire in establishing formalized stopping rules. Any data presented by treatment group at the DSMB meeting will be blinded with regard to the identity of the comparison groups, and participating investigators (except for the study biostatistician) will not see any data broken down by treatment group during the course of the trial.

9 RANDOMIZATION, DATA MANAGEMENT AND DATA MONITORING

The randomization of the patients and the processing and analysis of the data will be carried out by the lead study biostatistician ([name]) at University of Colorado. The randomization will be stratified by study site. Within each site, randomly selected block sizes of 2, 4, or 6 will be used so that the site investigators cannot predict beforehand the group to which the patient will be randomized.

Data collection will be performed using REDCap (Research Electronic Data Capture). REDCap is a secure web application for building and managing online surveys and databases. The software is available at no cost for REDCap Consortium Partners. The building of an online survey or database and the inputting of data can be done anywhere in the world over a secure web connection with authentication and data logging. The REDCap surveys and databases can be used by researchers from multiple sites and institutions. Confidentiality will be protected. REDCap is considered "Part 11 capable", meaning that the software has all the required features for compliance.

Timing of Ileostomy Closure after Ileal Pouch Surgery

We have built a REDCap database for this study using 8 forms per patient. These will include Form 1, Screening; Form 2, Pre-IPAA Data; Form 3, IPAA operative Details; Form 4, IPAA Assessment; Form 5, ostomy reversal details; Form 6, Complications; Form 7 – Functional Outcome & SF-12; Form 8, Adverse Events.

Study data for this study will be collected and stored using electronic records. Data captured will be entered in real time at each clinical site using web forms developed to replicate paper case report forms. All data will be created, modified, maintained, archived, retrieved and distributed by a computer system. The use of electronic records will increase the speed of data collection and exchange. This will reduce the manpower necessary to perform double-data entry from paper forms and transcription error. In addition, electronic records permit economical storage of study data and ease of accessibility and analysis. Data management and data quality systems will be built into the system.

Data quality using electronic records will ensure that data are attributable, legible, contemporaneous and original.

The biostatistics team at the University of Colorado will track the data collection, provide data security, control for confidentiality of study data, maintain computer backups to protect data until study closure and archive study data according to FDA requirements (21 CFR 11). Electronic signatures will be linked to each entry.

All computer systems and programs will be password protected, and all electronic communications of study and other confidential information will be encrypted. Personnel at the CGIBD have extensive training and experience using electronic data systems. Good computer security practice (restricting physical access to machines, prohibition of password sharing, and logging off computers after work hours or when away from the machine) will be required of all study personnel.

Only authorized persons are authorized for data entry and access. Data security systems require password protected identification codes for data entry and provide protection against data manipulation. The database is located on a server protected by firewalls. Access to the database server will not be allowed by users on computers outside of the firewall-protected zone. Virus protection software is installed on each study machine. System access to computer systems will be audited. Redundant backups and off-site backup storage will allow for quick restoration of data in the unlikely event that a hardware failure, disaster, or security breach should occur. Servers and backups will be located in a secured location with access limited to authorized personnel.

Data cleaning will include range and edit checks, cross form edit checks, query generating and tracking and periodic data status reports. Any data errors or inconsistencies detected after data entry will be automatically tracked, communicated and resolved using a web-based application. An audit trail of all data changes over the life of the study will be maintained. All study raw data, forms, documents, software programs, software applications and computer data files will be indexed and archived routinely. Strict version control of documents and software applications will be instituted. Retention of study documentation after study completion will be seven years after closure with the IRB. Standardized study

management reports will be generated monthly during the recruitment phase of the study. These reports will be used to track study progress including patient enrolment, randomization, compliance, patient status changes, and study events. The data will be reported for each Study Center individually and summarized for the study as a whole. A report will also be generated for the DSMB meeting. This report will include additional information on clinical events and adverse events that is coded by blinded treatment group. Other than the study statistician and statistical analyst, no study personnel will see this report.

10 STATISTICAL CONSIDERATIONS

Sample Size Calculation

The developers of the CCI consider a 10-point difference in their 0 to 100 morbidity scale to be clinically meaningful; it reflects a 1-grade difference in the established Clavien-Dindo classification of postoperative complications (Slankamenac, 2014; Clavien, 2009). They also report a standard deviation of the CCI of 20-22 in two surgical trials. Assuming 80% power and an $\alpha = 0.05$ level of significance, our trial would need about 63-76 patients per group, or a total of 126-152 patients to complete both phases of the trial. It is anticipated that up to 600 patients will be required for phase 1 due to the expected $\leq 75\%$ drop out of phase 1 patients who are not eligible for phase 2.

Statistical analyses

A Consort Diagram will be used to account for all patients screened for inclusion in the trial; those who were excluded and included and reasons for exclusion; those who were randomized; and those who were followed at each time point or who were lost to follow-up. The primary analysis will be by intention-to-treat, meaning that the patients will be analyzed by the group to which they were randomized. This means that patients randomized to the short interval closure group who have postoperative complications that delay closure will still be analyzed in the group to which they were randomized. Secondary analyses will be done per-protocol (analyzing patients who followed the protocol), and as-treated (analyzing patients by the treatment they actually received).

Patient baseline characteristics will be compared between the early and late closure groups using a chi-square test for categorical variables and a t-test for independent samples for normal continuous variables or a Wilcoxon two sample ranks test for non-normal continuous variables.

Complications will be reported using the Clavien-Dindo classification. Perioperative details in the two groups will be compared using the same methods as were used for comparing the patient baseline characteristics.

The primary analysis will be comparing Comprehensive Complication index and overall complication rates up to 6 months postoperatively between the two randomized groups using a generalized linear model with a log-link function with

Timing of Ileostomy Closure after Ileal Pouch Surgery

group (short vs. long interval closure) and hospital as the independent variables. We will also include any patient baseline characteristics that remained unbalanced in spite of randomization. Secondary analyses will include a comparison of mean number of complications per patient using a zero-inflated Poisson model, and a comparison of severe complications (Clavien-Dindo Grade IIIa or higher) using the same methods as were used for the primary analysis. We will also compare the mean number of stoma related complications using a zero-inflated Poisson model. Since the quality of life scales are continuous variables measured over time, we will compare the early vs. late closure groups for these outcomes using linear mixed models.

DSMB interim analyses and early stopping rules for interim analyses

At their first meeting, the DSMB will decide how they wish to monitor the study. Typically, a DSMB will monitor all aspects of a study to ensure its scientific integrity, including patient screening and accrual, follow up, performance of individual centers, data acquisition and quality issues, adverse events, and outcomes. At the first meeting, we will also determine their desire in establishing formalized stopping rules. Any data presented by treatment group at the DSMB meeting will be blinded with regard to the identity of the comparison groups, and participating investigators (except for the study biostatistician) will not see any data broken down by treatment group during the course of the trial.

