Secondary variables:	(1) Total number of postoperative complications per patient; (2) Percent of patients with complications; (3) Total number of stoma related complications per patient; (4) Health-related quality of life; and (5) IPAA functional outcomes (all at 6 months after randomization).
Statistical analysis:	
A Consort Diagram will be used to account for all patients screened for inclusion in the trial; those who were excluded and included and reasons for exclusion; those who were randomized; and those who were followed at each time point or who were lost to follow-up. The primary analysis will be by intention-to-treat, meaning that the patients will be analyzed by the group to which they were randomized. This means that patients randomized to the short interval closure group who have postoperative complications that delay closure will still be analyzed in the group to which they were randomized. Secondary analyses will be done per-protocol (analyzing patients who followed the protocol), and as-treated (analyzing patients by the treatment they actually received).
 
Patient baseline characteristics will be compared between the early and late closure groups using a chi-square test for categorical variables and a t-test for independent samples for normal continuous variables or a Wilcoxon two sample ranks test for non-normal continuous variables.
 
Complications will be reported using the Clavien-Dindo classification. Perioperative details in the two groups will be compared using the same methods as were used for comparing the

Timing of Ileostomy Closure after Ileal Pouch Surgery

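### The per-protocol and as-treated analyses select patients on complication-driven delay, which favors early closure when such delay falls mainly in the early arm

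*Combined protocol and SAP*

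**What the plan says.** Section 10, Statistical analyses, makes ITT the primary analysis. To explain it, the plan describes "patients randomized to the short interval closure group who have postoperative complications that delay closure" and keeps them in their randomized group. The next sentence reads: "Secondary analyses will be done per-protocol (analyzing patients who followed the protocol), and as-treated (analyzing patients by the treatment they actually received"). Section 1 has the same text, including "as-treated (analyzing patients by the treatment they actually received"). Neither section gives criteria for the two sets, adjusts for the reason for delay, or says how the results should be read.

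Section 3, Overview of time sequence, supplies the rest:

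- Randomization is on day 5-12 after pouch surgery, after clinical and radiologic clearance and before closure (item 6).
- Early closure is on day 7-12 (item 7a).
- Late closure is at 8-12 weeks in item 7b, but at 8 weeks or more with no upper limit in item 6 and in the Appendix timeline.
- Recording of complications for the CCI starts at randomization and runs to 6 months (item 8a).

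**The concern.** A complication after randomization that pushes closure past day 12 does two things. It raises that patient's CCI, and it takes the patient out of the early-closure window. On the plain reading of the per-protocol rule, the patient then leaves the early arm. Under the as-treated rule the patient may be moved to the late group. In both cases the early group loses patients with poor outcomes because of those outcomes. The plan names complication-driven delay only for the short-interval arm, so it describes no matching loss on the other side.

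At stake is how the secondary results are read. A comparison selected in this way can show fewer complications with early closure when timing has no effect, and the plan gives no warning of this.

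**Working it through.** **Step 1. The plan's own figure.** Section 10 gives the inputs: "The developers of the CCI consider a 10-point difference in their 0 to 100 morbidity scale to be clinically meaningful", and "They also report a standard deviation of the CCI of 20-22 in two surgical trials". With 80% power and alpha 0.05 (taken as two-sided; the plan does not say), n per group = 2 x (1.960 + 0.842)^2 x SD^2 / 10^2 = 2 x 7.849 x SD^2 / 100.

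- SD 20: 2 x 7.849 x 400 / 100 = 62.8, so 63 per group and 126 in total.
- SD 22: 2 x 7.849 x 484 / 100 = 76.0, so 76 per group and 152 in total.

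This matches the stated 63-76 per group and 126-152 in total. The 10-point target is the yardstick below.

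**Step 2. Bias with no timing effect.** Both arms have the same CCI distribution. A share f of the early arm has a complication that delays closure, and these patients score D points above the rest, whose mean is m. An equal share of the late arm has equally severe complications but stays within its window. Each arm then has mean m + fD.

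- ITT: (m + fD) - (m + fD) = 0.
- Per-protocol (delayed patients dropped): m - (m + fD) = -fD.
- As-treated (delayed patients counted as late): the late group's mean is [(m + fD) + f(m + D)] / (1 + f) = m + 2fD/(1+f), so the bias is -2fD/(1+f).

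Negative values favor early closure.

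**Step 3. Numbers.** The documents give neither f nor D. Assumed ranges are f = 5-20% and D = 10-30 points. False-positive rates come from 4,000 simulated trials per setting (76 per arm, total SD 22, unequal-variance test at 0.05).

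| f | D | Per-protocol bias | As-treated bias | Per-protocol false positives | As-treated false positives |
|---|---|---|---|---|---|
| 5% | 10 | -0.5 | -0.95 | 5.3% | 5.8% |
| 10% | 20 | -2.0 | -3.6 | 8.7% | 17.6% |
| 20% | 20 | -4.0 | -6.7 | 18.8% | 46.2% |
| 20% | 30 | -6.0 | -10.0 | 40.2% | 82.0% |

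On the same data ITT had bias near 0 and false-positive rates of 4.6-5.8%.

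**Step 4. How strongly must delay track the CCI?** Take an assumed CCI mean of 19 and SD of 22, 76 per arm and 10% delayed. If the chance of delay is proportional to the full 6-month CCI, the false benefit is about 2.6 points per-protocol (14% false positives) and 4.7 as-treated (28%). If instead every patient with a nonzero CCI is equally likely to be delayed (40% zeros assumed), it is about 1.5 points (7%) and 2.6 points (13%). The milder rule roughly halves the result. Delay unrelated to the CCI gives no bias.

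**Step 5. Departures in the late arm.** At f = 10%, D = 20 and 76 per arm:

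| Equally complicated late-arm patients | Per-protocol bias | As-treated bias |
|---|---|---|
| None depart | -2.0 | -3.6 |
| Half close after week 12 | -1.1 | -3.7 |
| Half close before week 8 | -1.0 | -1.7 |
| All close after week 12 | 0.0 | -3.7 |
| All close before week 8 | 0.1 | 0.1 |

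Departures in the late arm shrink the per-protocol bias, and full symmetry removes it. For as-treated, only closures before week 8 help.

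**The case against.** The strongest reply is that the primary result is protected. The sentence about delay illustrates the ITT rule, gives no frequency, and the other two analyses are labelled secondary. That stands. A reader might infer that these analyses will be used to confirm ITT, or to claim a benefit when ITT is null. Nothing in the documents says so.

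A reader might also infer that both analyses always favor early closure. The documents do not support that, for two reasons.

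- The as-treated direction depends on a rule the plan does not state. A patient closed between day 13 and week 8 received neither defined treatment. If such patients count as early, as-treated comes close to ITT.
- It cannot be assumed that nothing comparable happens in the late arm. Under the 8-12 week wording, a complication that pushes closure past week 12 also breaks protocol. The listed stoma complications might also lead to closure before week 8. Under the wording with no upper limit, a delay never takes a late-arm patient outside the window.

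The size is also open. Patients are randomized after clearance, and the gap to the end of the early window is at most 12 - 5 = 7 days. Only complications in that gap can delay closure beyond the window, so selection by the full 6-month CCI is a strong assumption and f may be small. At f = 5% and D = 10 the error rates are close to nominal.

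These points limit direction and size. They do not remove the defect: on its plain reading, the per-protocol rule excludes early-arm patients because of an event that is part of the outcome.

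**Conclusion.** The concern holds in conditional form. With no true effect, per-protocol favors early closure when complication-driven departures fall mainly in the early arm. As-treated does so too if delayed patients are counted as late, and its bias is then nearly twice as large, by the factor 2/(1+f). Over the assumed f of 5-20% and D of 10-30, the bias is about -0.5 to -6 CCI points per-protocol and about -1 to -10 as-treated, against a target of 10. These figures are illustrative, because they rest on f and D values that the documents do not supply. They also assume that no late-arm patient departs because of a complication. ITT is unbiased throughout. The point is a cheap improvement to the secondary analyses and does not threaten the primary conclusion.

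**What to change.** First reconcile the late-closure windows in Section 3 (items 6 and 7b) and the Appendix timeline. Until that is done, a per-protocol set cannot be defined. Then amend Sections 1 and 10:

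- **Per-protocol.** Patients in either arm whose closure fell outside the window because of a complication stay in their randomized arm. Exclude only departures unrelated to outcome, such as eligibility error or logistics. Do not move any patient between arms by actual closure date.
- **As-treated.** Drop it, or replace it with a complier-average estimate that uses randomized arm as the instrument. Label it supportive. State its assumption that assignment affects the CCI only through the closure-timing category, and say in advance how closure between day 13 and week 8 is classified. Intermediate closures strain that assumption, so the estimate should not carry more weight than ITT.

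The cost is wording and a little analysis work. The per-protocol result will lie closer to ITT and so add less to it. The complier-average interval is wider. With no early closures in the late arm it is roughly the ITT interval divided by (1 - f): 1/0.9 = 1.11 times as wide at f = 10%, and 1/0.8 = 1.25 times at f = 20%.
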